# 4.1 Efficacy Endpoints

Efficacy endpoints in this study include:

- o The number of subjects in each group with 20/40 or better BCVA at Day 28
- Central corneal thickness at Day 28

The following additional endpoints will also be assessed:

#### 4.2 Measures Taken to Minimize/ Avoid Bias

All adverse events will be recorded regardless of suspected causality. Additionally, subjects will be assigned to the open treatment group at the time of determination of eligibility dependent upon the subject's desire to receive investigational product. All subjects in all treatment groups are required to meet all eligibility criteria. All primary and secondary efficacy endpoints will be source data verified or provided by an independent 3rd party (e.g., central reader).

Confidential and Proprietary

Amendment 7.0: September 22, 2022

# 4.3 Study Treatment

# 4.3.1 TTHX1114 Drug Product

# 4.3.2 TTHX1114 Storage

# 4.3.3 TTHX1114 Preparation

# 4.4 Duration of the Study and Study Treatment

Each subject is expected to be on study for approximately 1 year following DWEK/DSO.

	Main Study		Optional Extended Dosing Period		
	# of	Duration	# of	Duration	
	injections	of Treatment	injections	of Treatment	
Group 1	-	-	-	-	
Group 1a	5	over 28 days	-	-	
Group 2	5	over 24 days			
Group 3	1	one time	4	over 21 days	
Group 3a	4	over 21 days	-	-	
Group 4	4 to 5*	over 21 to 28 days	1*	one time	

\*Subjects who received 5 injections in Group 4 are NOT eligible for OEDP

Clinical Study Protocol TTHX-002

Confidential and Proprietary

Amendment 7.0: September 22, 2022

# 4.5 Stopping Rules

Stopping rules for the study will be the incidence of unacceptable toxicity. This is an open-label study, and the frequency and severity of all adverse events will be monitored on an ongoing basis.

#### 4.6 Investigational Product Accountability

In accordance with 21 CFR 312.61 and 21 CFR 312.62(a), the Investigator

- Will administer the drug only to subjects under the investigator's personal supervision or under the supervision of a subinvestigator responsible to the investigator,
- Shall not supply the investigational drug to any person not authorized under this part to receive it, and
- Will maintain adequate records of the disposition of the drug, including dates, quantity, and use by subjects

If the investigation is terminated, suspended, discontinued, or completed, the investigator shall return the unused supplies of the drug to the sponsor, or otherwise provide for disposition of the unused supplies of the drug under 21 CFR 312.59.

#### 4.7 Data to be entered into the Database

The majority of data collected will be entered into the database via the EDC system. Data from 3rd parties (e.g., central labs or reading facilities) will be imported into the clinical database, these data include:

- Endothelial cell counts and characteristics assessed by the central reading center
- Pharmacokinetic measurements
- Anti-drug antibody assay results
- Clinical laboratory testing results

Imported data will be reconciled (e.g., Subject ID, date, time, timepoint) with the clinical database and the results will be uploaded into the database under a Quality and Data Transfer Specifications Agreement. Uploaded data will then be 100% quality checked with the data at the source.

Other data and results generated by the investigational site will be data entered directly into the electronic data capture (EDC) system. All data in the EDC will be monitored and critical variables will be 100% source data verified.

#### 5. SELECTION AND WITHDRAWAL OF SUBJECTS

Potential subjects will be identified on the basis of having a confirmed diagnosis of FECD and being a suitable candidate for DWEK/DSO. Most potential subjects will come directly from the patients receiving care at the investigational site. All subjects must be suitable for DWEK/DSO procedure independent of the clinical trial.

Amendment 7.0: September 22, 2022

Subjects who participated in Study TTHX-001 and who subsequently were scheduled for DWEK/DSO may be enrolled in Study TTHX-002 if they meet all eligibility criteria.

Subjects who participated in Study TTHX-001 and did not receive active study treatment (i.e., were assigned to the placebo treatment or only participated in the Observational Sub-study) may be included in any treatment group in Study TTHX-002.

Subjects who participated in Study TTHX-001 and received any dose level active study treatment (i.e., received 4 IC injections of TTHX1114) may be included in Group 3 of Study TTHX-002. Note: No subject can receive more than 5 cumulative administrations of TTHX1114. Subjects who received TTHX1114 in Study TTHX-001 can receive 1 additional dose in Group 3 but WILL NOT be eligible to roll-over to Group 3a.

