**Table 7: Study Groups and Number of Subjects** 

	TTHX1114	4 Regimen		
	Day	Dose	Number of Subjects	
Group 1	N/A	N/A	8 (Closed after 1 enrolled)	
	Day -3	10ng		
	Day 0	50ng	9.16	
Group 2	Day 7	10ng	8-16 (Closed after 9 enrolled)	
•	Day 14	10ng		
	Day 21	10ng		
Group 3	Day 0	100ng	20	
Group 4	Day 0	100ng	20	
	Day 7	30 or 50ng		
	Day 14	30 or 50ng		
	Day 21	30 or 50ng		
Group 1a	Weekly x 5	30 or 50ng	NA	
Group 3a	Weekly x4	30 or 50ng	NA	
·		 	up to 50	

[figure not shown]
Subject will be consented and screened for eligibility during the screening period prior to the scheduled DWEK/DSO procedure.

The study schema is presented in Figure 1 and Figure 2.

Confidential and Proprietary

Amendment 7.0: September 22, 2022

Figure 1: Study Treatment Schema

\*Subjects who have not sufficiently recovered by Day 28, may receive an additional dose of TTHX1114 following discussion with the Medical Monitor

Eligible subjects who do not wish to receive investigational product or who do not have a qualifying Fellow Eye will be assigned to Treatment Group 1.

Following preliminary safety and tolerability assessment of the 50ng IC injection in Group 2, Trefoil may elect to open Group 3 and Group 4

[figure not shown]
- Group 3 in which eligible subjects will be given a "1 and done" dosing regimen in which TTHX1114 will be administered as a 100ng/100mcL volume injection at the time of DWEK/DSO
- Group 4 in which eligible subjects will be given a 100ng/100mcL volume injection at the time of DWEK/DSO and then weekly injections of 30 or 50ng (30 or 50mcL) x3. Subjects in Group 4, who have not sufficiently recovered by Day 28, may receive an additional dose of TTHX1114 following discussion with the Medical Monitor

Following preliminary safety and efficacy evaluation in subjects who received TTHX1114, Trefoil may open enrollment in Groups 1a and 3a in which TTHX1114-naive subjects in Group 1 and subjects in Group 3 may be allowed to "roll-over" to a TTHX1114 regimen of up to 5 weekly injections of TTHX1114. To be eligible for Group 1a or Group 3a, subjects must continue to be eligible for the study (e.g., have a suitable fellow eye and not have had any severe suspected adverse reactions.

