# **Study Treatment Group 3a:**

Subjects in Group 3 may be allowed to "roll-over" to a TTHX1114 regimen of up to 4 weekly injections of TTHX1114. To be eligible for Group 3a, subjects must

- continue to be eligible for the study (e.g., have a suitable fellow eye and not have had any severe suspected adverse reactions)
- not have achieved adequate restoration of the endothelium (anatomic recovery) by the anticipated timepoint following the DWEK/DSO procedure (e.g., Day 56 or 84)
  - Note: the trigger for roll over to Group 3a may be earlier if the time to anatomic recovery observed in Group 2 or 3 is sooner

Subjects who had previous participated in Group 3 will receive up to 4 weekly study treatment administrations.

- Day 0
- Day 7
- Day 14
- Day 21

Follow-up visits will occur on:

- Day 28
- Day 56

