#### **Long-term Follow-up (All Treatment Groups)**

A subjects will undergo long-term follow-up for up to 1 year following the later of DWEK/DSO or the first TTHX1114 administration.

Amendment 7.0: September 22, 2022

- Long-term Follow-up visits will occur on: Day 84
- Day 168
- Day 336/ End of Study Visit

For subjects who have had both eyes treated on study, the Day 168 and Day 336 visits for both eyes may be combined calculated based on the date of surgery of the second eye. Day 336 is considered the End of Study Visit and includes a Comprehensive Eye Examination.

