#### 6.1.2 The Study Eye (SE)

The Study Eye (SE) will be determined by the Investigator prior to the clinical trial as eligibility for the study required a planned DWEK/DSO procedure planned for the medical management of the patient. The SE is defined as the eye that was selected by the treating physician for surgical intervention of DWEK/DSO and the eye to which TTHX1114 is administered (if applicable).

If a study subject wishes to undergo DWEK/DSO in the Fellow Eye after the SE has recovered, the subject may be re-enrolled in Group 3 or Group 4 and the contralateral eye may be treated. "Recovery" is based on the Investigator discretion following the primary efficacy endpoint evaluation on Day 28 (e.g., BCVA of at least 20/40 or have a measured CCT of less than a 10% increase from baseline). Planned treatment of all contralateral eyes must be discussed with and approved by the Sponsor (or designee) prior to treatment.

[figure not shown]

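### The limit of 5 TTHX1114 administrations per subject is not reconciled with second-eye treatment: 4 of 12 pathway combinations always exceed it

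*Combined protocol and SAP*

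**What the plan says.** **The limit.** Section 5 states: "No subject can receive more than 5 cumulative administrations of TTHX1114". The unit is the subject, and doses from the earlier trial count. A person who "received 4 IC injections of TTHX1114" in TTHX-001 "can receive 1 additional dose in Group 3 but WILL NOT be eligible to roll-over to Group 3a", which makes 4 + 1 = 5.

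**The second eye.** Section 6.1.2 says that once the first eye has recovered, "the subject may be re-enrolled in Group 3 or Group 4 and the contralateral eye may be treated". The opening of Section 4 assigns that eye by whichever groups are open at the time. The check in Section 6.1.2 is sponsor approval: "Planned treatment of all contralateral eyes must be discussed with and approved by the Sponsor (or designee) prior to treatment". Neither place refers to the limit or to the number of earlier injections. The long-term follow-up text in Section 4 treats the two eyes as belonging to one subject ("For subjects who have had both eyes treated on study").

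**The roll-over.** The design text after Table 7 in Section 4 offers Group 1 and Group 3 subjects together a "regimen of up to 5 weekly injections of TTHX1114". The Group 3a text later in Section 4 instead gives a "regimen of up to 4 weekly injections of TTHX1114". Table 7, the synopsis and the Table 6 schedule also show 4 for Group 3a.

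**The concern.** Section 5 states an exposure limit in absolute terms. Section 6.1.2 offers a treatment pathway that, for some subjects, cannot be completed without passing that limit. A site that follows Section 6.1.2 for a subject who finished Group 2 has no visible instruction telling it that the next injection would be the sixth.

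At stake are adherence to a stated exposure limit, the classification of protocol deviations, and the interpretation of safety data from subjects with two treated eyes. Without a clear counting rule, two reviewers could label the same sixth injection differently: one as permitted by Section 6.1.2, the other as a breach of Section 5.

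The roll-over sentence is a smaller, separate conflict. It arises within one eye, so counting the limit per eye would not remove it.

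**Working it through.** This is integer counting; no statistical formula is involved.

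**Inputs: injections per course**
- Group 1: 0 (Section 4, Group 1 text).
- Group 1a: up to 5 after 0 (Section 4, Group 1a text). With at least one injection, 1 to 5.
- Group 2: 5, on Days -3, 0, 7, 14 and 21 (synopsis; Table 2).
- Group 3: 1, on Day 0 (Table 7).
- Group 3a: up to 4 after 1 (Group 3a text; Table 7; synopsis; Table 6). With at least one roll-over injection, the eye total is 1 + (1 to 4) = 2 to 5.
- Group 4: 4, or 5 if the additional dose is given (Section 4, Group 4 text).

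**Step 1: the plan's own figure.** Single-eye totals are 0 (Group 1), 1 to 5 (1a), 5 (Group 2), 1 (Group 3), 2 to 5 (3 with 3a) and 4 to 5 (Group 4). TTHX-001 active treatment plus Group 3 is 4 + 1 = 5. Under the group-specific text, every single-eye path meets the limit of 5.

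**Step 2: add the second eye.** Total = first-eye course + second-eye course, where the second eye adds 1 (Group 3) or 4 to 5 (Group 4).

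| First eye | Second eye Group 3 | Second eye Group 4 |
|---|---|---|
| Group 1 | 0 + 1 = 1, within | 0 + (4 to 5) = 4 to 5, within |
| Group 1a | (1 to 5) + 1 = 2 to 6, may exceed | (1 to 5) + (4 to 5) = 5 to 10, may exceed |
| Group 2 | 5 + 1 = 6, always exceeds | 5 + (4 to 5) = 9 to 10, always exceeds |
| Group 3 | 1 + 1 = 2, within | 1 + (4 to 5) = 5 to 6, may exceed |
| Group 3 with 3a | (2 to 5) + 1 = 3 to 6, may exceed | (2 to 5) + (4 to 5) = 6 to 10, always exceeds |
| Group 4 | (4 to 5) + 1 = 5 to 6, may exceed | (4 to 5) + (4 to 5) = 8 to 10, always exceeds |

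Result: 4 always exceed, 5 may exceed and 3 stay within (4 + 5 + 3 = 12).

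**Step 3: the roll-over sentence.** For a Group 3 subject, the sentence after Table 7 gives up to 1 + 5 = 6 in one eye. The Group 3a text gives up to 1 + 4 = 5. Using the larger number in the table changes the row for Group 3 with 3a to 3 to 7 and 6 to 11; the 4/5/3 split does not change.

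**Step 4: how many subjects could be affected.** Table 7 shows Group 2 closed after 9 enrolled. Each of those 9 would pass the limit if the five injections were completed and a second eye were then treated. The documents do not say how many second eyes were treated.

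**The case against.** The strongest reply is that Section 5 prohibits while Section 6.1.2 only permits. A general permission can be read as subject to an absolute limit, and the sponsor must approve every second eye. Section 6.1.3 adds registration, enrolment approval and group assignment before drug is shipped, and its eligibility checklist already records earlier participation in TTHX-001 or TTHX-002. On this view the gap is a missing cross-reference.

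Much of this stands, and it lowers the severity. It does not close the gap, because neither control carries a visible criterion based on the cumulative count. If the limit does override, a subject who completed Group 2 could never use the second-eye option, and Section 6.1.2 states no such exception.

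The roll-over sentence can also fairly be called loose drafting. It covers Groups 1 and 3 jointly, and the other Group 3a entries all give 4. It is still current text that conflicts with them.

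Redaction matters too. Sections 5.1 and 5.2 are almost wholly removed, and material after the Section 6.1.2 text is not shown. A limit on re-enrolment could sit there, though it would not reconcile the two roll-over numbers.

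**Conclusion.** The inconsistency is real and should be fixed. Under the visible text, 4 of 12 first-eye by second-eye combinations cannot be completed within 5 administrations, and 5 more may pass it. The count assumes completed Group 2 and Group 4 courses, at least one injection in any roll-over, no further roll-over of the second eye, and no subjects actively treated in TTHX-001.

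Three stronger readings are tempting, and the documents do not support them.
- A reader might infer that most combinations, 9 of 14, always exceed the limit. That needs the roll-over courses to be fixed at their maximum, which moves three combinations (1a then 3, 1a then 4, 3 with 3a then 3) into the always group. It also needs the two second-eye combinations for subjects treated in TTHX-001: 4 + 3 + 2 = 9. The roll-over courses are maxima, and Section 5 already limits the TTHX-001 subjects to one more dose.
- A reader might infer that the protocol never gives the counting unit. Section 5 gives it as the subject. What is missing is confirmation that this wording was meant to cover both eyes once second-eye treatment was allowed.
- A reader might infer that Per Protocol membership is compromised. Table 12 does require all treatments per protocol, but no visible text places fellow eyes in that set; Section 9.3.1 mentions them only for adverse event listings. Any such effect is conditional on their inclusion.

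**What to change.** - Reconcile the opening of Section 4, the roll-over sentence after Table 7, the Group 3a text, Section 5 and Section 6.1.2, so that the limit and the second-eye and roll-over pathways agree. State whether the per-subject wording is intended to span both eyes. Use one number for Group 3a throughout. Which limit and which number apply is for the sponsor to decide.
- Add the cumulative administration count, including TTHX-001, to the registration and eligibility checklist in Section 6.1.3, to be checked before a second eye or a roll-over is approved.
- Tabulate cumulative administrations per subject and per eye in the safety report. If dosing is already complete, the tabulation and a stated rule for classifying totals above 5 as deviations are still needed.
- State whether fellow eyes enter the Per Protocol Set.

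The cost is protocol wording, one field on an existing form and one exposure table. Some second-eye pathways may turn out to be unavailable, depending on the sponsor's decision.

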#### 5.1 Inclusion Criteria

# 5.2 Exclusion Criteria

Planned post-operative rho-kinase inhibitor use

Amendment 7.0: September 22, 2022

Confidential and Proprietary

in the opinion of the Investigator could increase the subject's risk, interfere with the interpretation of the study results, or affect the subject's ability to provide informed consent or comply with the study

Amendment 7.0: September 22, 2022

# 5.3 Subject Withdrawal Criteria

Subjects will be discontinued from continued study treatment if any of the following occur:

- Intolerable side effects
- The Investigator feels it is in the subject's best interest
- Non-compliance
- Pregnancy

Subjects who are discontinued from study treatment are expected to remain on the study and complete all appropriate safety and efficacy assessments.

Subjects may withdraw from the trial at any time and for any reason.

If a subject withdraws from the trial, attempts should be made to contact the subject to determine the reason(s) for discontinuation while respecting the subject's privacy. All procedures and evaluations required by the final study visit should be completed in the event of early withdrawal. All subjects who discontinue the trial due to an adverse event must be followed until the event has resolved, returned to baseline, or stabilized (if resolution is not anticipated).

#### 6. TREATMENT OF SUBJECTS

This study will be conducted at qualified clinical investigational sites. Sites will be selected based on the ability to safely conduct the study and where Trefoil can be assured of patient safety and the ability to effectively monitor. Investigational sites should monitor health websites such as (https://www.cdc.gov/coronavirus/2019-ncov/index.html and https://www.aao.org/coronavirus) for up-to-date information and resources.

Investigational site staff are instructed to follow their institutional infection control standard procedures and to consider additional measures during periods of community transmission of conditions such as COVID-19. These additional measures may include:

- Contacting subjects, the day before a scheduled appointment
  - To determine if they are experiencing any signs or symptoms of possible infections, such as

Amendment 7.0: September 22, 2022

- Fever
- Cough
- Shortness of breath
- Sore throat
- To determine if the subject has tested positive for COVID-19, been in contact with someone who is known or suspected COVID-19, or traveled to an area of risk
- Rescheduling subjects who are experiencing respiratory symptoms and instructing them to seek appropriate medical attention
- Reminding subject to contact the investigational site if they develop respiratory symptoms on the morning before a scheduled examination or if they have had changes to their health status

Upon arrival at the investigational site, subjects should be

- Assessed for fever
- Provided with PPE (e.g., face masks)

Equipment that is meant to be used on more than one person should be draped to prevent possible contamination and appropriately cleaned before and after each use. Additional measures should also be considered such as:

- Posting guidelines
- Remind subjects of the need for social distancing/ consider having subjects wait outside of the investigational site (e.g., in their vehicles until ready to be seen)
- Non-essential individuals accompanying study subjects should not permitted in patient areas
- Provide supplies for respiratory hygiene and cough etiquette, including 60-95% alcohol-based hand sanitizer (ABHS), tissues, no-touch receptacles for disposal, face masks, and tissues at healthcare facility entrances, waiting rooms, patient check-ins, etc.
- Provide respiratory hygiene supplies such as tissue to cover cough and hands-free receptacle for refuse disposal
- Remind subjects to wash hands and/ or use hand sanitizer

Study visits and assessments should be rescheduled at the discretion of the Investigator when there is a perceived increased risk to study subjects and/or investigational site staff.

#### 6.1 Subject Screening and Enrollment

Potential study participants will be asked to sign an Informed Consent Form (ICF) prior to any study assessments. Screening should be completed within approximately 28 days of Study Day 0 (unless approved by the Medical Monitor); non-qualifying screening assessments (e.g., specular microscopy) and screening assessments outside this window may be repeated. Screening assessments will include:

Assessment of study eligibility

Confidential and Proprietary

Amendment 7.0: September 22, 2022

- Medical and ocular history
- BCVA assessment
- Comprehensive ocular examination (including slit lamp biomicroscopy and dilated examination of lens, fundus, and vitreous)
- Specular microscopy (including images of the central and peripheral cornea)

All potential study subjects will be provided with a unique Subject ID Number (Subject ID) at the time of providing written informed consent. The Subject ID will consist of a unique 6-digit number (3-digit site number and a 3-digit subject number, separated by a hyphen [-]).

Figure 3: Subject ID Numbering

Subject ID Number						
Site Number			=	Subject Number		
9	9	9	-	2	0	1

For example, Subject ID 101-201 = The first participant consented at Site 101; 103-203 = The third participant consented at Site 103

Once a Subject ID number has been issued, it cannot be reused. Potential subjects may have repeat eligibility assessments (if appropriate) or be rescreened, following discussion with the Medical Monitor (or designee).

Subjects who had participate in Study TTHX-001 will receive a new Subject ID number for identification in Study TTHX-002. Subjects who "roll-over" to Group 1a or Group 3a will retain the same Subject ID number.

# 6.1.1 Descemetorhexis without Endothelial Keratoplasty (DWEK)/ Descemet Stripping Only (DSO)

Patients with FECD who have a planned DWEK/DSO or DMEK procedure will be evaluated for eligibility in this study. As the DWEK/DSO procedure is not a study procedure DWEK/DSO will be done according to institutional policy with a descemetorhexis area of 4 to 5mm. The method of surgery many include the use of the Sinskey Hook (with or without forceps) or an irrigation/aspiration (I&A) tip. The method of surgery will be at the discretion of the Investigator and Investigators will be selected based on their demonstrated expertise (e.g., historical number of procedures and relative success rate). The Lead Investigator may assist in the selection of investigational sites and the vetting of Investigators. Only qualified and vetted ophthalmologists will perform the surgical procedure on subjects enrolled in this study to minimize operator variability. Subjects with a descemetorhexis area of > 5mmwillbe excluded from efficacy analyses but will be included in the safety analyses.

AS-OCT should be performed at least 1 time following DSO (e.g., Day 28) to confirm the size of the descemetorhexis area, especially in subjects with delayed recovery.

Amendment 7.0: September 22, 2022

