✓ DWEK DSO Procedure ↑ TTHX1114 administration	Study Design	Open label, single treatment, with a concurrent non-treatment control in patients with FECD undergoing DWEK/DSO procedure.  • Group 1 (No TTHX1114)  ○ DWEK/DSO: Day 0  • Group 2: TTHX1114 in combination with DWEK/DSO  ○ DWEK/DSO: Day 0  ○ TTHX1114: Day (-3), 0, 7, 14, and 21  • Group 3: TTHX1114 in combination with DWEK/DSO  ○ DWEK/DSO: Day 0  ○ TTHX1114: Day 0  • Group 4  ○ DWEK/DSO: Day 0  ○ TTHX1114: Days 0, 7, 14, 21  • Group 1a  ○ TTHX1114 weekly x 5  • Group 3a  ○ TTHX1114 weekly x up to 4  TTHX-002 Study Schema  Group 2  □ S 0 1 7 14 21 28 56  □ DWEK/DSO  □ TTHX1114 ↑ ↑ ↑ ↑ ↑ ↑ ↑ ↑ ↑ ↑ ↑ ↑ ↑ ↑ ↑ ↑ ↑ ↑

[figure not shown]
Confidential and Proprietary

Amendment 7.0: September 22, 2022

Confidential and Proprietary

Amendment 7.0: September 22, 2022

Confidential and Proprietary

Amendment 7.0: September 22, 2022

Table 1: Schedule of Events Group 1

Si	tudy TTHX-	002: G	roup 1						
	Screening (≈28 days	0*	1	14 (±1)	28 (±3)	56 (±3)	84 (±21)	168 (±21)	336 (±21)
Informed Consent	X			\	( - )		(/	(/	(/
Demographics	X								
Medical and Ocular History	X								
Comprehensive Ocular Examination (including slit lamp examination and dilated exam of the lens, fundus, and vitreous)	SE				SE	SE			
Slit Lamp Biomicroscopy	SE a	SE	SE	SE	SEa	SEa			
Specular Microscopy	SE			SE	SE	SE			SE
Assessment of Corneal Thickness b	SE	SE		SE	SE	SE	SE	SE	SE
Best-corrected Visual Acuity	SE	SE	SE	SE	SE	SE	SE	SE	SE
Intraocular Pressure (IOP) Measurement	SE	SE	SE	SE	SE	SE			
Optional Blood for Genetic Testing		X							
V-FUCHS	X				X	X			
DWEK/DSO		X							
Collect Endothelium Tissue sample		X							
Collect Aqueous Humor sample		X							
Concomitant Medications Review	X	X	X	X	X	X			
Assess Adverse Events		X	X	X	X	X			

OU=both eyes, SE=Study Eye, V-FUCHS=Visual Function and Corneal Health Status

Note: Unless otherwise specified assessments to be performed prior to study treatment injection, if applicable \*Day 0 pre-treatment ocular assessments may be obtained within the 7 days prior to Day 0 (if screening visit assessments were within 7 days, they do not need to be repeated)

<sup>a as part of Comprehensive Eye Examination

<sup>b measured by AS-OCT (preferred) if AS-OCT not available, Pentacam or Ultrasound Pachymetry is to be used (Note: subjects must be assessed using the same modality throughout the study)

Confidential and Proprietary

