### 6.4.11 Delayed Recovery

Subjects with delayed recovery should undergo additional ocular assessments at Day 28, Day 56, or at unscheduled visits. These assessments may include:

- Additional; methods of BCVA (See Section 6.4.8)
- Central Corneal Thickness (by the primary or alternative method)
- AS-OCT
- Pentacam
- etc.

Additional ocular assessments should be reported as an Unscheduled Visit (See Section 6.5.5)

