**Table 12: Analysis Sets** 

Analysis Set	Description of Population	Reference
Full Analysis Set*	
 
Received any study treatment (at least 1 complete or partial dose)
 
	ICH E9 (5.2.1)
Per Protocol Set	Met all eligibility criteria	ICH E9 (5.2.2)
	Have received all study treatments per protocol	
	
 
Underwent DWEK/DSO of 4 to 5mm
 
	
	
 
Have sufficient data collected for the accurate assessment of study endpoints
 
	

\*The Full Analysis Set will be used for the Safety Population

The Per Protocol Population will be used to assess the primary and secondary efficacy endpoints compared to the control group.

The Safety Population set includes all participants in participants who received any TTHX1114 and will be the population for safety outcomes; this population will be compared with the control group. Ocular AEs involving the study eye will be tabulated. Ocular AEs for the fellow eye and non-ocular AEs will be provided as a listing.

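### Eyes over 5 mm leave the only stated efficacy population after surgery, and the sizing scan is aimed especially at slow-recovering eyes, which can inflate Day 28 success

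*Combined protocol and SAP*

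**What the plan says.** Section 6.1.1 specifies a descemetorhexis of 4 to 5 mm and states that subjects above 5 mm are "excluded from efficacy analyses but will be included in the safety analyses". It then sets out the check on size: "AS-OCT should be performed at least 1 time following DSO (e.g., Day 28"), with the stated aim "to confirm the size of the descemetorhexis area, especially in subjects with delayed recovery".

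Table 12 in Section 9.3.1 makes "Underwent DWEK/DSO of 4 to 5mm" a condition of the Per Protocol Set. Below the table: "The Per Protocol Population will be used to assess the primary and secondary efficacy endpoints compared to the control group". The Full Analysis Set is assigned to safety, and no efficacy analysis on it is stated.

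Section 4.1 lists as efficacy endpoints "The number of subjects in each group with 20/40 or better BCVA at Day 28" and central corneal thickness at Day 28. Section 7 makes Day 28 the primary efficacy timepoint. Section 4 describes the study as open label.

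Section 6.4.11 adds: "Subjects with delayed recovery should undergo additional ocular assessments at Day 28, Day 56, or at unscheduled visits". AS-OCT is one of several assessments that these may include. That section does not mention descemetorhexis size or analysis sets.

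Tables 1 to 6 have no row for AS-OCT sizing. AS-OCT appears there as the first choice for corneal thickness: "measured by AS-OCT (preferred) if AS-OCT not available, Pentacam or Ultrasound Pachymetry is to be used" (Table 1, footnote b).

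**The concern.** Size acts here as an entry criterion for efficacy that is applied after surgery. That raises two separate problems.

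**Uneven detection.** Section 6.1.2, when discussing treatment of the fellow eye, illustrates recovery as BCVA of at least 20/40 or a corneal thickness less than 10% above baseline. These are the same measures as the Day 28 endpoints. The available text does not define delayed recovery separately, so in practice it overlaps with failing the endpoint. An instruction to look for oversize especially in those eyes directs the search for a reason to exclude towards the failures, at about the time when the outcome becomes known to an unmasked site.

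**Selection by size itself.** Even if every eye is measured equally well, removing oversize eyes raises the reported rate if those eyes recover less often. No all-treated result is stated against which to judge this.

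The documents state no safeguard for the size reading. The bias measures in Section 4.2 cover the endpoints. The list of imported third-party data in Section 4.7 does not include size. The reading centre's task in Section 6.4.6 is specular images. Because Group 1 closed after 1 subject (Table 7), the efficacy evidence rests mainly on within-group rates, and those are what this selection alters.

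**Working it through.** The plan has no figure of its own to reproduce. Section 9.1 says the sample size is not statistical, and no success, oversize or detection rate is given. The only document input below is the 20 subjects planned for each of Groups 3 and 4 (Table 7). Everything else is assumed for illustration.

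**Formula.** With 12 successes and 8 failures among 20 eyes, all failures sized, and a share *d* of successes sized:

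reported rate = (12 − excluded successes) / (20 − all excluded)

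**A. Oversize 20% whatever the outcome.** Excluded failures = 8 × 0.20 = 1.6. Excluded successes = 12 × 0.20 × *d* = 2.4*d*.

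| Successes sized | Calculation | Reported rate | Added to 60.0% |
|---|---|---|---|
| 100% | 9.6 / 16.0 | 60.0% | 0 |
| 90% | 9.84 / 16.24 | 60.6% | 0.6 |
| 80% | 10.08 / 16.48 | 61.2% | 1.2 |
| 30% | 11.28 / 17.68 | 63.8% | 3.8 |
| 0% | 12 / 18.4 | 65.2% | 5.2 |

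All of the movement in A comes from uneven detection.

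**B. Oversize 40% in failures and 10% in successes.** Excluded failures = 8 × 0.40 = 3.2. Excluded successes = 12 × 0.10 × *d* = 1.2*d*.

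| Successes sized | Calculation | Reported rate | From the restriction | From uneven detection |
|---|---|---|---|---|
| 100% | 10.8 / 15.6 | 69.2% | 9.2 | 0 |
| 30% | 11.64 / 16.44 | 70.8% | 9.2 | 1.6 |
| 0% | 12 / 16.8 | 71.4% | 9.2 | 2.2 |

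**C. Range when size has no effect on recovery.** Let *p* be the success rate, *L* the oversize share and *d* the share of oversize successes identified, with all oversize failures identified:

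reported rate = [(1−*L*)*p* + *Lp*(1−*d*)] / {[(1−*L*)*p* + *Lp*(1−*d*)] + (1−*L*)(1−*p*)}

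Over *p* = 0.4 to 0.8, *L* = 0.1 to 0.3 and *d* = 0 to 0.5, the inflation runs from +0.9 points (*p* = 0.8, *L* = 0.1, *d* = 0.5: 0.76/0.94 = 80.9%) to +8.8 points (*p* = 0.4, *L* = 0.3, *d* = 0: 0.40/0.82 = 48.8%). At *d* = 1 it is zero throughout.

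**D. Whole eyes.** From 12/20 = 60.0%, removing one failure only gives 12/19 = 63.2%. Removing two gives 12/18 = 66.7%.

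**Size range, side by side.** The exclusion sentence in Section 6.1.1 removes eyes above 5 mm only. Table 12 requires 4 to 5 mm. An eye below 4 mm is untouched by the first and removed by the second.

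**The case against.** The strongest reply is that Section 6.1.1 asks for AS-OCT at least once in every subject. The phrase about delayed recovery adds emphasis to that request and does not restrict it. If every eye is sized, case A gives 60.0% and there is no detection bias. AS-OCT is also the preferred thickness method and corneal thickness is scheduled at Day 28 in Groups 1 to 4, so many recovered eyes would be imaged anyway. This stands: detection bias depends on compliance. It is not a complete answer, because the request is a recommendation with no fixed visit, thickness may be measured by other devices, and nothing says that thickness scans are used for sizing.

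A reader might infer that failures are in fact preferentially removed and that success is in fact inflated, or might credit the whole rise of about 11 points in case B to outcome-driven detection. The documents support neither. They give no rates, and 9.2 of those points come from restricting to 4 to 5 mm eyes, which can be defended as a choice of target population.

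Three further limits hold. Section 6.4.11 says only that assessments may include AS-OCT and does not link them to exclusion. The word confirm in Section 6.1.1 is compatible with a size already noted at surgery, and whether one is recorded cannot be judged because the Day 0 procedure text is not available. The two size statements can both be applied at once, with Table 12 the stricter, so that part is a reconciliation of wording.

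**Conclusion.** The concern holds as a risk that the plan leaves open. Exclusion from the only stated efficacy population is decided after surgery, by a measurement whose completeness can depend on the outcome, in an open-label study. This can inflate Day 28 success.

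The size of the bias is unknown. Under the assumptions in case A, uneven detection adds 0 points if all successes are sized, 3.8 if 30% are and 5.2 if none are. Under the assumptions in case B, the restriction by itself adds 9.2 points even with complete sizing, and uneven detection adds a further 1.6 to 2.2 when 30% or none of the successes are sized. Total bias is zero if sizing is complete and size does not affect recovery.

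The effect falls mainly on within-group rates. A difference in bias between groups cannot be shown, because the documents give no enrolment dates to set against the introduction of the size rule. The full SAP that Section 9.3 promises before database lock is not among the documents and might address some of this.

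**What to change.** 1. In Section 9.3.1 and the SAP, make the main Day 28 efficacy result the one in all treated eyes whatever the descemetorhexis size, with the 4 to 5 mm restriction as a sensitivity analysis. List size exclusions by group and recovery status. Amend the exclusion sentence in Section 6.1.1 to match.
2. For the sensitivity analysis, use a size fixed without regard to outcome. This can be the size recorded at surgery, if available, or the AS-OCT that Section 6.1.1 already requests, taken at one fixed visit in all subjects, entered in the schedules, and read without knowledge of BCVA, thickness or recovery status. State that extra imaging of delayed-recovery eyes does not determine analysis-set membership. Such imaging for care may continue.
3. Reconcile Section 6.1.1 with Table 12 so that eyes under 4 mm are handled one way.

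The cost is protocol and SAP wording, one schedule entry if the fixed-visit scan is used, and masked reading of scans already requested. The downside is that the headline rate may be slightly less favourable, because it will include some oversize eyes.
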